9.3.1.2 Enrolled Subjects

Subjects who are randomized to receive study drug treatment are considered enrolled subjects.

9.3.2 Study Day

Study Day, which follows the CDISC SDTM standard, is defined as (Assessment date of first study drug dosing + 1 day), where the assessment date is on or after the date of first study drug dosing; (Assessment date - date of first study drug dosing), where the assessment date is before the date of first study drug dosing.

9.3.3 End of Study Treatment Definition

A subject is considered to have completed study treatment if the subject has completed the Week 12 Visit.

9.3.4 End of Study Definition

A subject is considered to have completed the study if the subject has completed the 30 day Follow-up Visit.

9.3.5 Age

Age (years) will be calculated as the number of years between year of birth and year of informed consent, rounded down to the largest to a whole number less than or equal to the age at measurement.

9.3.6 Body Mass Index

Body mass index (BMI, kg/m²) is derived as weight (kg) / [height (m) × height (m)].

9.3.7 Baseline Values

Baseline values are defined as the last non-missing assessment prior to the first dose of randomized, double-blind study drug in the study.

9.3.8 Change from Baseline

Change from baseline is calculated as the post-baseline assessment subtracted by the baseline assessment.

9.3.9 Percent Change from Baseline

Percent change from baseline is calculated as the change from baseline divided by the baseline assessment and multiplied by 100%. This value will be rounded to two decimal places unless otherwise stated.

9.3.10 Log-transformed Change from Baseline

The log-transformed change from baseline is calculated as the difference of the log(post-baseline assessment) subtracted by the log(baseline assessment). It is also mathematically equivalent to calculate the log-transformed change from baseline as the log of the ratio of the post-baseline assessment divided by the baseline assessment.

$$\begin{aligned} \text{log-transformed change from baseline} \\ &= \log(\text{post-baseline assessment}) - \log(\text{baseline}) \\ &= \log \left(\frac{\text{post-baseline assessment}}{\text{baseline assessment}} \right) \end{aligned}$$

9.3.11 Upper Limit of Normal or Target by Efficacy Biomarker

The key biomarker upper limit of normal (ULN) and Target values that are displayed in [Table 2](#) will be used in data analysis. The age at screening will be used to determine those age-specific ULN values.

Table 2 Upper Limit of Normal Values by Subgroup and Key Biomarker

Baseline Characteristic	DHEAS ULN	ACTH ULN	17-OHP Target	A4 ULN
$\geq 18 - \leq 30$ years	377 $\mu\text{g}/\text{dL}$	63.0 ng/dL	200 ng/dL	200 ng/dL
$\geq 31 - \leq 40$ years	295 $\mu\text{g}/\text{dL}$	63.0 ng/dL	200 ng/dL	200 ng/dL
$\geq 41 - \leq 50$ years	240 $\mu\text{g}/\text{dL}$	63.0 ng/dL	200 ng/dL	200 ng/dL

9.3.12 Responder Definitions

The second secondary efficacy and exploratory variables are proportions of responders based on serum DHEAS assessments. Indicator variables will be created for the responder criteria as follows:

Table 3 Responder Definition by Endpoint

Endpoint	Definition
Proportion of subjects with at least a 30% reduction from baseline in DHEAS dose [1]	$\begin{cases} 1 & \geq 30\% \text{ reduction in DHEAS} \\ 0 & < 30\% \text{ reduction in DHEAS OR missing} \end{cases}$
Proportion of subjects with DHEAS \leq ULN	$\begin{cases} 1 & \text{DHEAS} \leq \text{ULN} \\ 0 & \text{DHEAS} > \text{ULN OR missing} \end{cases}$
[1] repeat same definition for 25% and 20% reduction	

9.3.13 Geometric Mean Ratio and Percent Change

For efficacy hormone variables ([Section 5.2.2.1](#)), the geometric mean ratio (GMR) and percent change from baseline will be calculated by treatment group and dose level. The GMR is derived from the natural logarithm of the post-baseline value divided by the baseline value [$\log(\text{post-baseline}/\text{baseline})$]. The GMR is the exponential function of the mean of $\log(\text{post-baseline}/\text{baseline})$. The 95% CI of GMR is the exponential function of the 95% CI of the mean [$\log(\text{post-baseline}/\text{baseline})$]. The percent change is derived as $100 \times (\text{GMR} - 1)$. The 95% CI of percent change is $100 \times (95\% \text{ CI of GMR} - 1)$.

9.3.14 Study Drug Exposure Variables

9.3.14.1 Study Drug Compliance per Treatment Period

Study drug compliance is defined as the percentage of study drug actually taken compared to what was expected based on the randomized or titrated dose for time period i (where subject is receiving a constant dose). Using the drug accountability data, study drug compliance is calculated as follows:

$$\%Compliance_i = 100 \times \left(\frac{\# Dispensed - \# Returned - \# Lost or Destroyed}{\# Expected tablets to be taken} \right)_i$$

and total % compliance over a treatment period is calculated as:

$$\%Compliance = 100 \times \left(\frac{\sum_{i=1}^k (\# Dispensed - \# Returned - \# Lost or Destroyed)_i}{\sum_{i=1}^k (\# Expected tablets to be taken)_i} \right)$$

where

Σ represents the summation operator and the value in parentheses is summed over the sequence $i = 1$ to k , where

k = number of time intervals subject is receiving a constant dose. Possible constant dose levels are placebo, 50 mg QD tildacerfont, 100 mg QD tildacerfont, or 200 mg QD tildacerfont. At 50 mg QD tildacerfont dose level, 1 active tablet and 3 placebo tablets are taken per administration (i.e., 4 tablets per day); at 100 mg QD tildacerfont dose level, 2 active tablets and 2 placebo tablets are to be taken per administration (i.e., 4 tablets per day); at 200 mg QD tildacerfont, 4 active tablets are to be taken per administration (i.e., 4 tablets per day).

The expected number of tablets to be taken is the number of expected tablets per day (4 tablets) multiplied by the number of days in time period i .

9.3.14.2 Total Tildacerfont Dose (mg) Taken

Total tildacerfont dosage (mg) is defined as the dosage of tildacerfont taken over a specific study period i (where subject is receiving a constant dose), calculated as follows:

$Total Tildacerfont Dose_i$

$$= ((\# Dispensed - \# Returned - \# Lost or Destroyed) \times Tablet Strength)_i$$

and total tildacerfont dose over the entire study period is calculated as:

$$\text{Total Tildacerfont Dose} = \sum_{i=1}^k (\text{Total Tildacerfont Dose})_i$$

where

Σ represents the summation operator and the value in parentheses is summed over the sequence $i = 1$ to k , where k = number of time intervals subject is intended to receive study drug, and Tablet strength is 0 mg if placebo or 50 mg, 100 mg, 200 mg tildacerfont if active drug.

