Clinic visits will occur at the following times:

- Optional DHEAS Screening Visit
- Screening Visit (Safety labs and assessments, inclusion/exclusion criteria evaluation, medical history, and concomitant medications)
- Treatment Period:
 - Period 1: At Day 1 and Day 28
 - Period 2: Day 56
 - Period 3: Day 84
- Follow-up: At 30 days after the last dose of study drug

Clinic visits should be scheduled for the early morning, to accommodate morning laboratory assessments (approximately 8 A.M. \pm 1 hour). DHEAS is expected to peak in the morning after overnight ACTH surge, so morning draws are optimal for the DHEAS Screening Visit. However, any previously documented DHEAS elevation will confirm eligibility during the optional pre-screening visit.

Telephone Contacts

Sites will make scheduled telephone contacts to all subjects at Weeks 2, 6, and 10 to assess for the occurrence of AEs and the initiation of new concomitant medications.
 
Subjects should be instructed to telephone sites if they have any concerns about their health and/or to report AEs.

Duration of Subject Participation: Approximately 25 weeks, inclusive of up to 30 days of optional DHEAS screening, 30 days of screening, 12 weeks of treatment, and 30 day follow up.

Planned Sample Size and Number of Sites: This study will enroll approximately 40 subjects at approximately 15 investigative sites within North America.

Study Drug and Route of Administration: Tildacerfont, an oral small-molecule corticotropin-releasing factor type-1 (CRF₁) receptor antagonist will be supplied as 50 mg tablets. Placebo will be supplied as tablets that look identical to drug product but contain no drug substance.

Subject Population: Female subjects 18 to 40 years old with PCOS and screening DHEAS levels that exceed the age-matched reference ULN threshold.

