5.2.2. Formulation, Appearance, Packaging, and Labeling

The drug product tildacerfont (SPR001) is formulated as a tablet containing 50 mg of drug substance. Tildacerfont tablets are round and convex in shape and yellow in color and will be packaged into blister cards.

Placebo will be supplied as tablets that look identical to the drug product but contain no drug substance.

All study treatment packaging (both drug product and placebo) will be labeled with the protocol number, recommended storage conditions, name and address of the Sponsor, an Investigational Use Statement (eg, "Caution: New Drug – Limited by Federal [USA] Law to Investigational Use"), and the instruction that the agent should be kept out of the reach of children. Labeling will comply with all legal requirements and supply no information about individual subjects.

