9.3.14.4 Mean Daily Tildacerfont Dose (mg/day)

Mean Daily tildacerfont Dose (mg/day) is calculated as Total tildacerfont Dose (mg) divided by Treatment Duration (days) for each treatment period and over the entire study.

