9.3.17 Subject-Level Study Treatment

This study consists of Screening, Treatment, and Follow-up periods. For a data record, the planned treatment and dose level will be based on a specific study period as follows:

Study Period	Planned Treatment
Screening	Placebo or tildacerfont (50 mg QD)
Treatment Period (Day 1 to Week 4)	Placebo or tildacerfont (50 mg QD)
Treatment Period (post-Week 4 to Week 8)	Placebo or tildacerfont (100 mg QD)
Treatment Period (post-Week 8 to Week 12)	Placebo or tildacerfont (200 mg QD)

The actual study drug treatment and dose level will be the study drug and dose level a subject was on when a data record was measured/assessed.

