12 STUDY DRUG AND OTHER MEDICATIONS

12.1 Exposure to Study Drug and Study Treatment Compliance

Summaries of study drug exposure and compliance will be summarized overall and separately for each dose level of the Treatment Period. The source for study drug dosing and compliance is drug accountability.

The summaries will include the total number of doses taken, mean daily dose (mg/day), duration (days) of exposure, and study drug compliance (see definitions in [Section 9.3.13.1](#)) by treatment group. A subject who received multiple dose levels of tildacerfont will be included in each of the dose levels for the purpose of summarization.

The drug accountability information, including number of tablets dispensed, number of tablets returned, and number of tablets lost or destroyed, along with all summarized variables, will be listed in subject listings.

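### The total tildacerfont dose formula (SAP 9.3.14.2) multiplies a tablet count by the daily dose level instead of the 50 mg tablet strength, inflating mean daily dose 3.0- to 4.0-fold for a fully compliant completer

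*SAP*

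**What the plan says.** SAP 9.3.14.2 takes tablets dispensed, minus those returned, minus those lost or destroyed, multiplies by tablet strength within each constant-dose period, and sums over periods. It specifies the multiplier: "Tablet strength is 0 mg if placebo or 50 mg, 100 mg, 200 mg tildacerfont if active drug".

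The protocol describes a single active product. Section 5.2.2 says "The drug product tildacerfont (SPR001) is formulated as a tablet containing 50 mg of drug substance", and the synopsis says that tildacerfont "will be supplied as 50 mg tablets". No 100 mg or 200 mg tablet appears in either document.

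SAP 9.3.14.1 explains how the dose levels are made up under the blind. "At 50 mg QD tildacerfont dose level, 1 active tablet and 3 placebo tablets are taken per administration"; the 100 mg level uses two of each; and "at 200 mg QD tildacerfont, 4 active tablets are to be taken per administration". Every subject takes 4 tablets a day throughout.

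SAP 9.3.14.4 divides total dose by duration, for each period and for the whole study, to give mean daily dose. SAP 12.1 reports it overall and by dose level: "The summaries will include the total number of doses taken, mean daily dose (mg/day), duration (days) of exposure, and study drug compliance". The same section lists the summarised variables by subject, and its accountability counts are numbers of tablets.

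**The concern.** The values 100 and 200 mg are what a subject receives in a day, not what one tablet contains. At those levels the tablet count already reflects that more than one tablet is taken daily, so using the daily dose as the per-tablet strength counts the dose again.

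The count is also undefined. The same expression is the numerator of the compliance formula in 9.3.14.1, where it covers all 4 daily tablets, active and placebo. Section 9.3.14.2 does not say whether the 0 mg value applies to each placebo tablet or only to the placebo arm, nor whether the two tablet types are counted separately.

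At stake is the exposure table that gives context to the safety results. Protocol 1.3 describes tildacerfont as expected to be generally well tolerated up to 200 mg QD and reports transaminase elevations at 400 and 1000 mg QD. A table showing an overall mean of 350 to 467 mg/day, or 800 mg/day at the top level, would misstate the exposure behind the safety data. SAP Section 4 makes the SAP govern where it and the protocol disagree on planned analyses, so the protocol's 50 mg tablet does not automatically correct the formula.

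**Working it through.** **Inputs.** Active tablet 50 mg (Protocol synopsis and 5.2.2). Active tablets per day 1, 2 and 4, out of 4 tablets a day (SAP 9.3.14.1). Multiplier 50, 100 and 200 mg (SAP 9.3.14.2). Four weeks per level (SAP Section 5), taken as 28 days each, 84 in all. Full compliance is assumed.

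**Reproducing the plan's dose levels.** Active tablets × 50 mg: 1 × 50 = 50, 2 × 50 = 100 and 4 × 50 = 200 mg/day. These match the stated levels, so 50 mg is the strength consistent with the tablet scheme.

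**Completer, total dose.**
- True: 28 × 50 × (1 + 2 + 4) = 9,800 mg; ÷ 84 = 116.7 mg/day.
- As written, active tablets only: 28 × (1×50 + 2×100 + 4×200) = 29,400 mg; ÷ 84 = 350 mg/day; ratio 3.0.
- As written, all tablets: 28 × 4 × (50 + 100 + 200) = 39,200 mg; ÷ 84 = 466.7 mg/day; ratio 4.0.

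**By dose level (mg/day).**

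| Level | True | Active tablets only | All tablets |
|---|---|---|---|
| 50 mg QD | 50 | 1 × 50 = 50 (1.0×) | 4 × 50 = 200 (4.0×) |
| 100 mg QD | 100 | 2 × 100 = 200 (2.0×) | 4 × 100 = 400 (4.0×) |
| 200 mg QD | 200 | 4 × 200 = 800 (4.0×) | 4 × 200 = 800 (4.0×) |

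**Shorter exposure.**
- Stopping at Week 8: true 28 × 50 × 3 = 4,200 mg (75 mg/day over 56 days). As written, active only: 28 × (50 + 200) = 7,000 mg (125 mg/day, 1.67×). All tablets: 28 × 4 × 150 = 16,800 mg (300 mg/day, 4.0×).
- Stopping at Week 4: true 1,400 mg (50 mg/day). As written: 1,400 mg (1.0×) or 28 × 4 × 50 = 5,600 mg (200 mg/day, 4.0×).

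On the active-only count, the size of the error therefore depends on how long a subject stays on treatment.

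**Sensitivity.** Period lengths of 27/28/28 or 28/28/29 days give 3.01× and 3.02× on active tablets, and 4.0× on all tablets.

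**Correcting the strength alone is not enough.** With 50 mg applied to all tablets, the completer total is 84 × 4 × 50 = 16,800 mg, or 200 mg/day at every level and 1.71 times the true total. The count must be restricted as well.

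**The case against.** The best defence is that a sensible reading exists. If the count meant daily doses, the formula would give 28 × (50 + 100 + 200) = 9,800 mg, which is right. But 9.3.14.1 and 12.1 both count tablets, so that reading fails. A programmer could instead apply 50 mg to each active tablet and 0 mg to each placebo tablet, which also gives 9,800 mg, but only by ignoring the 100 and 200 mg values that the SAP lists.

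A second defence is that little depends on the result. Mean daily dose is descriptive and no hypothesis test uses it. SAP Section 4 limits the SAP to topline results and an abbreviated report and sends dose-exposure-response work to a separate plan. Each subject's actual dose level is defined independently in 9.3.17. An 800 mg/day row should be spotted on sight. All of this stands and limits the consequence. It does not make the derivation correct, and an inflated overall mean or a 200 mg/day figure at the 100 mg level is less conspicuous.

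It is also fair that 3.0 and 4.0 are what literal coding would produce under two possible counts, not reported results, and that they concern the tildacerfont arm only. With 0 mg read by arm or by tablet, a placebo subject correctly gets 0 mg.

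**Conclusion.** The formula is wrong as written. For a fully compliant tildacerfont completer with 28 days at each level, literal application gives 350 or 466.7 mg/day against a true 116.7 mg/day, and 800 mg/day at the 200 mg level on either tablet count. The completer ratios of 3.0 and 4.0 do not depend on the level of compliance, provided the same share of active and of placebo tablets is taken in every period.

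The contradiction itself is certain. The size of any error in a reported table depends on which tablets are counted, which the SAP leaves open.

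The effect is confined to total dose, mean daily dose and the corresponding listing. Compliance, exposure duration, attribution of adverse events to dose level (9.3.17.1) and the efficacy analyses do not use total milligrams. The total number of doses named in 12.1 is not defined there, so nothing firm can be said about it; if it is a simple count, it is unaffected.

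**What to change.** In SAP 9.3.14.2, define total tildacerfont dose as active tablets taken × 50 mg, with each placebo tablet at 0 mg and the two types counted separately. Remove 100 and 200 mg from the list of tablet strengths.

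If accountability does not separate the types, use (tablets taken ÷ 4) × the daily dose level received in that period. SAP 9.3.17 already supplies that level: "The actual study drug treatment and dose level will be the study drug and dose level a subject was on" when the record was measured. State the assumption that missed tablets fall proportionally on active and placebo tablets, and state its limit. One missed tablet is costed at 50 ÷ 4 = 12.5 mg at the 50 mg level and 100 ÷ 4 = 25 mg at the 100 mg level, when the truth is 0 or 50 mg. At the 200 mg level the fallback is exact.

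As an illustration, with 11 of 112 tablets missed in a period:
- 50 mg level: 101 ÷ 4 × 50 = 1,262.5 mg; possible range (28 − 11) × 50 = 850 to 28 × 50 = 1,400 mg.
- 100 mg level: 101 ÷ 4 × 100 = 2,525 mg; possible range (56 − 11) × 50 = 2,250 to 56 × 50 = 2,800 mg.
- 200 mg level: 101 ÷ 4 × 200 = 5,050 mg, the same as 101 × 50.

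The cost is one SAP sentence and one derivation line, plus the stated assumption if the fallback is needed. This corrects a derivation and changes nothing about dosing.

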9.3.14.3 Study Drug Exposure Duration (days)

The duration (days) of study drug exposure is derived from the first dose date and the last dose date of a given period of time. Specifically, the duration (days) is calculated as (LASTDAY - FIRSTDAY + 1 day), where LASTDAY is the date of last dose, and FIRSTDAY is the date of first dose.

The date of the first dose is captured by the eCRF question, “Date of first dose?” The first dose date at the 100 mg tildacerfont QD and 200 mg tildacerfont QD is presumed to be the same as the dispensed date at the Week 4 and Week 8 visits, respectively.

The last dose date can be the last dose date of a treatment dose level or treatment end date.

9.3.14.4 Mean Daily Tildacerfont Dose (mg/day)

Mean Daily tildacerfont Dose (mg/day) is calculated as Total tildacerfont Dose (mg) divided by Treatment Duration (days) for each treatment period and over the entire study.

9.3.15 Prior, Concomitant and Post treatment Medications

A prior medication is considered to be any medication that is taken within a year prior to the first randomized, double-blind study drug dosing.

A concomitant medication (CM) is considered to be any medication that is continued after the first study drug dosing (i.e., a prior medication can also be a CM if it continued after the first dose of study drug) or any medication with start dates or stop dates within the Treatment Period. Specifically, CMs are medications: that are continued from Screening and continued after the first study drug dosing, or with start dates or stop dates within the first dose date through last dose date + 24 hours, missing CM end date, or ongoing with the study drug administration.

Post medications is considered to be any medication taken after the last study drug dose date + 24 hours, missing CM end date, or ongoing.

9.3.15.1 Prohibited Concomitant Medications

Prohibited and cautionary concomitant medications are those medications with their potential for metabolic interactions with tildacerfont. Specific definitions can be found in Protocol [Sections 5.6.1 and 12.3](#).

9.3.16 Adverse Events

AEs are those AEs with onset date from the signing of the ICF until the end of the follow up period.

Treatment-emergent adverse events (TEAEs) are defined as any AEs, regardless of relationship to study drug, that have an onset or worsening in severity on or after the first dose of study drug until 30 days after the final dose of study drug (Follow-up visit). For AEs that occur on the date of the first dose of study drug, the time of onset (before or after intake of study drug) will be specified and used for comparison.

If a subject discontinues study drug but remains in the study, AEs with onset date after 30 days of last dose of study drug until the end of the follow up period will be considered post-treatment adverse events.

Related TEAEs are those reported by investigators as possibly related, probably related, or definitely related to the study drug.

AESIs are events that do not meet SAE criteria but must be monitored on an ongoing basis as defined in Protocol [Section 7.2.8](#) and identified in the AE eCRF page.

Serious AEs (SAEs) are defined in Protocol [Section 7.2.6](#) and identified in the AE eCRF page.

Dose-limiting toxicities are defined as a Common Terminology Criteria for Adverse Events (CTCAE) Grade 3 or higher TEAE that is also considered at least possibly related to study drug.

Suspected unexpected serious adverse reactions (SUSARs) is an AE that is serious, related to study drug, and is not expected in the targeted disease (PCOS).

